7.3.2 Sensitivity Analyses

7.3.2.1 Lesion Count Variable Missing Data Imputation

The first sensitivity analysis for absolute change in lesion count will use a repeated measures ANCOVA, with factors of treatment group, analysis center, visit (i.e., Week 4, Week 8) and treatment group by visit interaction and a covariate of baseline lesion count. In this analysis, data from all post-baseline visits will be included with no imputation for missing data.

The second sensitivity analysis will use the model-based multiple imputation method to impute missing data for the absolute change in lesion counts at Week 12. The imputation model will include treatment group, analysis center, and baseline lesion count. A total of 2 random seeds will be needed to impute inflammatory lesion counts and non-inflammatory lesion counts for the two treatment groups. Those 2 random seeds have been pre-specified by using a random number generator:

- Inflammatory Lesion CountsSeed= 1134935092;
- Non-Inflammatory Lesion Counts: Seed= 1601290001.

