11.8 Sensitivity Efficacy Analyses

Sensitivity analyses for absolute change in lesion count

The first sensitivity analysis for absolute change in lesion count use a repeated measures ANCOVA, with treatment, analysis center, and visit (ie, Week 4, Week 8) as independent factors and a covariate of baseline lesion count. In this analysis, data from all post-baseline visits will be included with no imputation for missing data.

The second sensitivity analysis will use the model based multiple imputation method to impute missing data for the absolute change in lesion counts at Week 12. Although the full details will be presented in SAP the Multiple imputation will involve 4 principal tasks:

- 1. Calculate the number of missing values (nmiss) for absolute change in lesion count.
- 2. Missing values will be filled in '5 x nmiss' times to generate '5 x nmiss' complete data sets. The imputation model used will be an ANCOVA with factors of treatment group and analysis center, and a covariate of baseline lesion count (ie, the imputation model will be the same as the analysis model). Appropriate modifications will be made should the analysis be based on a non-parametric method.
- 3. Each complete data set will be analyzed with an ANCOVA with factors of treatment group, and analysis center, and a covariate of baseline lesion count.
- 4. Results from these analyses will be combined into a single inference.

Sensitivity analyses for IGA

The first sensitivity analysis for the dichotomized IGA success will use a repeated measures logistic regression model (generalized estimating equations), with dichotomized IGA success as the dependent variable and treatment, analysis center, and visit (ie, Week 4, Week 8) as independent factors. In this analysis, data from all post-baseline visits will be included with no imputation for missing data.

The second sensitivity analysis will use the model based multiple imputation method to impute missing data for the dichotomized IGA data. Although the full details will be presented in SAP, the multiple imputation will involve 4 principal tasks:

- 1. Calculate the number of missing values (nmiss) for absolute change in lesion count.
- 2. Missing values will be filled in '5 x nmiss' times to generate '5 x nmiss' complete data sets. The imputation model used logistic regression with factors of treatment group and analysis center (ie, the imputation model will be the same as the analysis model).

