5. CHANGES IN THE CONDUCT OF THE STUDY OR PLANNED ANALYSES

There are no changes in the conduct of the study, but there are minor changes to the planned analyses.

The pooling analysis described in the protocol is updated in the statistical analysis plan (SAP) to reflect the intended analysis. The protocol discusses pooling sites with five or fewer subjects enrolled in each treatment arm. Taking into consideration the randomization ratio, the SAP requires ten subjects in the active treatment arm and five subjects in the vehicle group. The SAP also clarifies the pooling of sites will be performed for each country separately.

As part of the pooling analysis, the treatment effect within investigational site must be investigated. The protocol states the site main effect will be examined by using a one-way analysis of variance (for lesion count variables) or a logistic regression analysis (for dichotomized IGA) with a factor of site. The SAP instead explains site will be incorporated into the primary analysis models. Change from Baseline in lesion counts will be analyzed with an analysis of covariance (ANCOVA) (unranked or ranked) with factors of treatment group, investigational site and treatment group by investigational site interaction, and the respective baseline lesion count variable as a covariate. The dichotomized primary endpoint will be analyzed with a logistic regression with factors of treatment group, investigational site and the interaction term of treatment group by investigational site.

The protocol describes repeated measures sensitivity analyses for the primary efficacy endpoints. Treatment group, analysis center and visit are listed as factors for the repeated measures analyses. In addition to these factors, the SAP includes a factor of treatment group by visit interaction.

A subgroup summary of oral contraceptive used was added. Specifically, subjects will be categorized as Oral Contraceptives Approved for Acne Treatment Usage and No Oral Contraceptives Approved for Acne Treatment Usage.

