7.2 Adjustments for Covariates

Baseline inflammatory lesion count will be a covariate for the primary efficacy endpoint for inflammatory acne lesion counts. Similarly, baseline non-inflammatory lesion count will be a covariate for the primary efficacy endpoint for non-inflammatory lesion counts. No other covariates are planned to be used in the analyses for this study.

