7.3 Handling of Dropouts or Missing Data

Missing 12 week efficacy data will be imputed and subsequently analyzed. The primary method of handling missing efficacy data will be the method of MCMC multiple imputation which does not rely on the assumption of data missing at random. Additionally, the pattern of missing observations in each treatment group will not influence the missing value estimation in the other because the imputation will be conducted independently for each treatment group.

The multiple imputation process for imputing missing lesion count and IGA data and subsequent analysis will involve 4 distinct phases with these principal tasks:

- 1. Calculate the number of missing 12-week values for each treatment group to be estimated by MCMC. Let nmiss be the maximum number of missing between the two treatment groups.
- 2. Create a data set of subjects, one for each treatment group, with observed values and those needing estimation by MCMC. The missing values in each data set will be filled in using the MCMC method '5 x nmiss' times to generate '5 x nmiss' data sets. The resulting data sets for each treatment arm will be combined into one complete data set for each imputation.
- 3. For each complete data set, compute the necessary derived variables. Each complete data set will be analyzed with the appropriate analysis model. See Sections 7.3.1.1 and 7.3.1.2 for details.
- 4. The results from these analyses will be combined into a single inference using SAS PROC MIANALYZE.

Sensitivity analyses will be performed on the primary efficacy endpoints to investigate the impact of the method of imputation. The first set of sensitivity analyses will use repeated measures. See Sections 7.3.2.1 and 7.3.2.2 for details.

The second set of sensitivity analyses will use model-based multiple imputation. The model-based multiple imputation process requires the data to have a monotone missing pattern. However, the imputation model will include treatment group and analysis center, and for lesion counts will include a covariate of baseline lesion count. Since treatment group, analysis center and baseline lesion count will be non-missing, the data will have a monotone missing pattern. The model-based multiple imputation process will involve 4 principal tasks:

- 1. Calculate the number of missing 12-week values to be imputed (nmiss).

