Note that interaction and skewness p-values will be computed for each imputation of multiply-imputed data. Model determination will depend on averaged p-values, computed by finding the mean p-values across all imputations.

The proportion of subjects who are dichotomized to success at Week 12 will be analyzed using a logistic regression with factors of treatment group and analysis center.

The sensitivity analysis for absolute change in lesion count will include a skewness test, based on the methods presented by J.H. Zar (1984) [1]. A ranked repeated measures analysis of covariance with factors of treatment group, visit, analysis center and treatment by visit interaction, and the respective baseline lesion count as covariate will also be included. Values will be ranked across all visits (i.e. visit will be ingored when ranking) and the baseline covariate will not be ranked.

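### The repeated-measures check on lesion counts imposes one baseline slope on all visits, which can cost a little Week 12 precision and, under arm-differential baseline-related dropout, bias the contrast either way

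*SAP*

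**What the plan says.** SAP 7.3.2.1 fits a repeated-measures ANCOVA to absolute change in lesion count. The factors are treatment group, analysis center and visit, completed by "treatment group by visit interaction and a covariate of baseline lesion count". No baseline-by-visit term is listed.

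The other descriptions of the model agree:

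- Protocol 11.8 has treatment, analysis center and visit "as independent factors and a covariate of baseline lesion count", with no interaction.
- SAP 5 records one change to that model: "In addition to these factors, the SAP includes a factor of treatment group by visit interaction".
- The ranked version in SAP 7.9.7.1 has "treatment by visit interaction, and the respective baseline lesion count as covariate will also be included". Ranks are pooled over visits and the baseline count is left unranked.
- SAP 7.2 closes with "No other covariates are planned to be used in the analyses for this study".

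SAP 7.3 gives the purpose: "Sensitivity analyses will be performed on the primary efficacy endpoints to investigate the impact of the method of imputation".

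The visits are less clear. The model sentence gives "visit (i.e., Week 4, Week 8" as the levels of the factor, yet the next sentence says that "data from all post-baseline visits will be included with no imputation for missing data". The schedule of events (Protocol Appendix 1) has post-baseline lesion counts at Weeks 4, 8 and 12. Week 12 therefore enters only by inference. Neither a Week 12 contrast nor a covariance structure is stated.

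**The concern.** The response is absolute change. Suppose a subject's count falls by a fraction f of baseline by a given visit. The change is then −f × baseline, and the slope of change on baseline is −f. If f grows over 12 weeks, the slope steepens from visit to visit, and a single slope is wrong at Week 12. The trial itself uses this proportional scale, since percent change is a secondary endpoint. Entry requires at least 20 lesions of each type with no upper limit, so baseline counts may vary widely.

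The other two analyses do not have this constraint. The primary ANCOVA is fitted to Week 12 change, and the second sensitivity analysis imputes Week 12 change from treatment, center and baseline. A gap between the repeated-measures result and the primary result could therefore come partly from the baseline adjustment and not only from the handling of missing data. A likelihood-based repeated-measures analysis also copes with dropout that depends on observed data only if its mean model is right, and dropout related to baseline is the simplest such case.

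**Working it through.** **1. The plan's own figures.** SAP 4.2 gives differences of 15.21 − 9.70 = 5.51 (SD 11.00) and 14.73 − 9.70 = 5.03 (SD 16.72), two-sided alpha 0.05. Power is approximately Φ(difference/SE − 1.96), with SE = SD × √(1/n₁ + 1/n₂).

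- Inflammatory, 300/150: SE = 11.00 × 0.1000 = 1.10; 5.51/1.10 = 5.01; power 99.9% (plan: at least 95%).
- Non-inflammatory, 450/225: SE = 16.72 × 0.0816 = 1.365; 5.03/1.365 = 3.68; power 95.8% (plan: 95%).

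The design figures reproduce. The plan states no figure for the repeated-measures model. At the planned 467/233, √(1/467 + 1/233) = 0.0802, so the unadjusted SEs are 0.88 and 1.34.

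**2. Precision with complete data.** With an unstructured covariance (assumed) and one common slope b, in large samples:

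- Week 12 estimate = raw difference − b × baseline imbalance
- SE ratio, common versus visit-specific slope = √(1 + (b₁₂ − b)² × k²), where k = baseline SD / Week 12 residual SD

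The documents give neither the slopes nor k. For slopes −0.3/−0.4/−0.5 with b near the middle value, the gap is 0.1: k = 1 gives √1.01 = 1.005 and k = 2 gives √1.04 = 1.020. For −0.2/−0.4/−0.6 the gap is 0.2: k = 1 gives 1.020 and k = 2 gives √1.16 = 1.077. Evaluated over the assumed baseline SDs and correlations, the ranges were 0.5 to 2.2% and 1.9 to 8.5%. An extreme set, −0.1/−0.4/−0.7, gave 4 to 18%. Equal slopes give zero. A chance baseline imbalance of one SE moves the estimate by 0.09 to 0.28 lesions, in either direction.

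**3. Direction of bias under dropout.** Ignoring what the model borrows from earlier visits, bias ≈ (b₁₂ − b) × D, where D is mean baseline in active minus mean baseline in vehicle among those still observed. With a gap of −0.1, D = +3 lesions (high-baseline vehicle subjects leave) gives −0.3, toward active. D = −3 gives +0.3, toward vehicle. These D values are illustrative. The sign comes from the dropout pattern and the slope trend, not from the omitted term alone.

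**4. Simulation at 467/233.** Unstructured covariance was used, with 300 trials per scenario in the first five rows. Where stated, missingness was about 15 to 19%. Slopes, baseline SD, correlations and dropout are all assumptions. The shift is in lesions at Week 12; negative favours active.

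| Assumed slopes, Weeks 4/8/12 | Endpoint | SE change | High-baseline vehicle subjects leave | High-baseline active subjects leave |
|---|---|---|---|---|
| −0.25/−0.40/−0.50 | Inflammatory | +1.2 to +5.6% (this row and the next) | −0.20 | not run |
| −0.15/−0.25/−0.33 or −0.15/−0.30/−0.45 | Non-inflammatory | as above | −0.30 to −0.50 | not run |
| −0.3/−0.4/−0.5 | Inflammatory | −0.2 to +1.1% (this row and the next) | −0.34 | +0.33 |
| −0.3/−0.4/−0.5 | Non-inflammatory | as above | −0.54 | +0.53 |
| −0.2/−0.4/−0.6 | Non-inflammatory | about +3 to +4% | −1.04 | +1.08 |
| Steepening, separate run | Inflammatory | about +1 to +3% (this row and the next) | −0.16 | +0.16 |
| Steepening, separate run | Non-inflammatory | as above | −0.40 | +0.39 |

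In the scenarios of rows three to five:

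- With dropout unrelated to baseline, related equally in both arms, or driven by lack of response, the mean shift was −0.06 to +0.04.
- With slopes that shrink over time, the signs reversed (+1.03 and −1.07, non-inflammatory).
- Opposite baseline-related dropout in the two arms was the most extreme case: about 0.5 (inflammatory) and 0.8 to 1.7 (non-inflammatory), again in either direction.
- With the baseline-by-visit term, the residual bias under one-arm dropout was about 0.02 for steepening slopes and at most 0.11 for shrinking slopes. The Monte Carlo error there is about 1.35/√300 = 0.08.

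Analysis center was left out of these simulations, and the ranked version was not simulated.

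**5. What the precision loss means.** For non-inflammatory lesions at 467/233, 5.03/1.341 = 3.75, so power is 96.3%. An SE 1% larger gives 3.71 and 96.0%. An SE 4% larger gives 3.61 and 95.0%.

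**The case against.** The strongest reply is that this is one of two supportive analyses and nothing confirmatory depends on it. That stands. The primary analysis is arm-specific imputation followed by a Week 12 ANCOVA, and the secondary testing order in SAP 7.6 does not use the repeated-measures model. A larger standard error makes a supportive analysis conservative and does not create false support.

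It is also fair to say that every size above is assumed. The documents give no baseline SD, visit slopes, correlations or dropout rate. SAP 4.2 mentions dropouts and withdrawals without a figure or an arm.

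Three stronger readings are tempting, and the documents support none of them:

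- *The omission favours the active arm.* That needs steepening slopes and loss of high-baseline subjects mainly from vehicle. The mirrored pattern moves the estimate toward vehicle by nearly the same amount, and nothing in the plan says which arm would lose such subjects.
- *The Week 12 standard error is inflated as a matter of course.* The effect depends on unequal slopes. In one simulated case the ratio was slightly below one (0.998).
- *A gap between this check and the primary result cannot be attributed to imputation at all.* The check already differs from the primary in other ways: a treatment-by-center term may enter the primary model, and the ranked version pools ranks over visits. The missing term adds one avoidable difference and is not the only one.

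What remains is that the constraint is specified, sits in only one of the three analyses, and is cheap to remove.

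**Conclusion.** The point holds as a modest improvement to a sensitivity analysis. SAP 7.3.2.1 and 7.9.7.1 impose one baseline slope on all post-baseline visits, while the primary ANCOVA has its own Week 12 slope.

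- If true slopes differ by visit, the cost is usually a Week 12 standard error roughly 1 to 4% larger in plausible cases.
- If baseline-related dropout also differs by arm, the bias may go either way. For inflammatory lesions it is about 0.2 to 0.3 (0.2/5.51 = 4% to 0.3/5.51 = 5% of the planned difference). For non-inflammatory lesions it is about 0.3 to 1.0 (0.3/5.03 = 6% to 1.0/5.03 = 20%). Against the unadjusted SEs of 0.88 and 1.34, that is about 0.2 to 0.3 SE and 0.2 to 0.7 SE.
- Without arm-differential, baseline-related dropout, the mean bias is about zero.

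These sizes rest on assumed slopes, baseline spread, dropout and an unstructured covariance. They also assume that Week 12 is in the model. The visit list as written leaves that open, and it is the more basic ambiguity in the same sentence.

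**What to change.** In SAP 7.3.2.1, add a baseline lesion count by visit interaction to the repeated-measures ANCOVA. In the same edit, list the visits as Weeks 4, 8 and 12, name the Week 12 treatment contrast as the result to be reported, and state the covariance structure. Carry the interaction into the ranked version in SAP 7.9.7.1 for consistency, noting that its effect there was not computed. Record the change in SAP 5 beside the treatment-by-visit term already listed.

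The cost is two degrees of freedom (three visits minus one) among about 700 subjects, plus SAP wording. No new data are needed. The extra term will not make missing-data handling the only difference from the primary analysis, but it removes one difference that serves no purpose.

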7.3.2.2 IGA Missing Data Imputation

The first sensitivity analysis for the dichotomized IGA success will use a repeated measures logistic regression model (generalized estimating equations), with dichotomized IGA success as the dependent variable and treatment group, analysis center, visit (i.e., Week 4, Week 8) and treatment by visit interaction. In this analysis, data from all post-baseline visits will be included with no imputation for missing data.

The second sensitivity analysis will use the model-based multiple imputation method to impute missing data for the dichotomized IGA data at Week 12. The imputation model used will be a logistic regression with factors of treatment group and analysis center. One random seed will be needed to impute IGA for the two treatment groups. The random seed has been pre-specified by using a random number generator:

• IGA: Seed= 977235733.

7.4 Interim Analyses and Data Monitoring

No interim analysis or data monitoring is planned for this study.

7.5 Multicenter Studies

The clinical study will be conducted under a common protocol for each investigational site with the intention of pooling the data for analysis. Every effort will be made to promote consistency in study execution at each study site. The study is intended to be conducted in a manner such that a minimum of 15 subjects will be randomized and included in the ITT population (i.e., at least ten subjects in the active treatment arm and five subjects in the vehicle treatment arm) for any investigator. In the event that there are too few subjects in a treatment arm for an investigational site, then the site's data will be combined with other site's data to achieve the desired sample size minimum per treatment arm. Country will be considered when pooling sites, such that sites from the United States will be combined with other sites from only the United States, and similarly for sites from Canada and sites from Australia. The combining of investigator data will be accomplished by taking the investigator with the smallest enrollment and combining it with the investigator with the largest enrollment, restricted to investigational sites who did not meet minimum enrollment. If there is a further need to combine data, then the data of the investigator with the second smallest enrollment will be combined with the investigator's data which had the second largest enrollment (restricted to investigational sites who did not meet minimum enrollment), and so on. This process will continue for all investigators who did not have a minimum of 15 subjects enrolled. The process of combining investigator data that have insufficient subjects per treatment arm will result in redefining the groups of investigators for the purposes of statistical analyses. These combined groups will be referred to as "analysis centers" in the statistical analyses.

The consistency of treatment response will be investigated across the analysis centers subsequent to combining the data as described above. Statistical tests will be conducted to identify if there are extreme analysis centers that could affect the interpretation of common statistical and clinical conclusions. An analysis center by treatment interaction will be included in the primary and secondary variable analyses to test for parallel treatment effect at an alpha level of 0.10. Change from baseline in inflammatory lesions and non-inflammatory lesions will be analyzed with an ANCOVA (unranked or ranked) with factors of treatment group, analysis center and treatment group by analysis center interaction and the respective baseline lesion count variable as a covariate. For the purpose of testing consistency of treatment response, the dichotomized IGA will be analyzed with a logistic regression with factors of treatment group, analysis center, and the interaction term of treatment group by analysis center. Further examination will follow for any variables that have a significant ANCOVA or logistic regression interaction term.

In the event that the ANCOVA or logistic regression interaction (referred to henceforth as the "appropriate test") p-value is ≤ 0.10 , a sensitivity analysis that excludes analysis centers with the extreme efficacy result will be performed to determine the robustness of the treatment effect. On the other hand, if all three analyses result in interaction terms with p-values > 0.10, then the

conclusions from the pooled data will be considered to be free of the impact of extreme analysis centers.

The first step in conducting a sensitivity analysis is to identify the extreme analysis center or centers that contribute to the statistical significance of the interaction term of the appropriate test. The process involves submitting subsets of analysis centers to the appropriate test and observing the interaction p-value for the subset. Subsets producing interaction p-values >0.10 are considered homogeneous.

The search for an extreme analysis center begins by analyzing all subsets that can be created by excluding one analysis center. If one or more of the subsets result in an interaction p-value >0.10, then the analysis center excluded from the subset with the largest interaction p-value is deemed to be the extreme analysis center.

If all subset interaction p-values are ≤ 0.10 , then the process will analyze the interaction for all subsets that can be created by excluding two analysis centers. If one or more of these subsets generate interaction p-values > 0.10, then the analysis centers excluded from the subset with the largest interaction p-value are deemed the extreme analysis centers.

Thus, the process of identifying the extreme analysis centers will continue in a stepwise manner by first excluding one, then two, then three, etc., analysis centers until the appropriate test interaction p-value is > 0.10.

Once the extreme analysis center or centers have been identified, then the treatment p-values of the remaining analysis centers will be computed. Inferences will be drawn from the treatment p-value, as well as any pertinent observations regarding the extreme analysis center or centers. Additionally, it is noted that this process excludes subjects from the analysis in a nonrandom manner and has an unpredictable impact on the power of the treatment effect test. In the event that the treatment effect of the remaining subset is not statistically significant, due consideration of the post hoc aspects of the process will be given when the results are interpreted. Conclusions will be presented by the Sponsor as appropriate to the findings of the sensitivity analysis.

Prior to investigating the treatment effect within the analysis centers, the treatment effect within investigational site will be investigated to determine if the site-to-site variability is such that it could mask the analysis center effects. Thus, prior to pooling, change from baseline in inflammatory lesions and non-inflammatory lesions will be analyzed with an ANCOVA (unranked or ranked) with factors of treatment group, investigational site, and treatment group by investigational site interaction, and the respective baseline lesion count variable as a covariate. The dichotomized primary endpoint will be analyzed with a logistic regression with factors of treatment group, investigational site, and the interaction term of treatment group by investigational site. If any of the analyses are not computationally feasible due to some investigational sites having very few subjects enrolled, the low-enrolling investigational sites will be excluded from the analysis.

